# **Statement of Compliance**

This study will be conducted in accordance with the International Conference on Harmonisation guidelines for Good Clinical Practice (ICH E6), the Code of Federal Regulations on the Protection of Human Subjects (45 CFR Part 46), and Thomas Jefferson University research policies

#### **List of Abbreviations**

AE Adverse Event/Adverse Experience

CBC Complete Blood Count

CFR Code of Federal Regulations

CIOMS Council for International Organizations of Medical Sciences

CONSORT Consolidated Standards of Reporting Trials

CRF Case Report Form

CRO Clinical Research Organization

CTCAE Common Terminology Criteria for Adverse Events

DSMC Data and Safety Monitoring Committee

DSMP Data and Safety Monitoring Plan
ECOG Eastern Cooperative Oncology Group

FACT-An The Functional Assessment of Cancer Therapy-Anemia

FDA Food and Drug Administration

FWA Federal wide Assurance
GCP Good Clinical Practice

GWAS Genome-Wide Association Studies

HIPAA Health Insurance Portability and Accountability Act

HRQoL Health-Related Quality of Life

IB Investigator's Brochure
ICF Informed Consent Form

ICH International Conference on Harmonization

IDE Investigational Device Exemption

IND Investigational New Drug Application

IRB Institutional Review Board MDS Myelodysplastic Syndrome

MedDRA Medical Dictionary for Regulatory Activities

MOP Manual of Procedures

N Number (typically refers to participants)

NCI National Cancer Institute
NIH National Institutes of Health

OHRP Office for Human Research Protections

PHI Protected Health Information

PI Principal Investigator

PRC Protocol Review Committee

QA Quality Assurance
QC Quality Control
RBC Red Blood Cell

SDS Safety Data Sheet (formerly MSDS; Material Safety Data Sheet)

SKCC Sidney Kimmel Cancer Center SOP Standard Operating Procedure TJU Thomas Jefferson University

UAP Unanticipated Problem

# Study Summary

Title: Measuring Physical Activity in Transfusion Dependent Patients

with Myelodysplastic Syndrome (MDS)

**Précis:** This will be a single-arm, prospective, observational study that

will collect data on daily step count, heart rate, and anemiarelated symptoms in patients with red blood cell transfusion
dependent MDS. Patients will be provided with a wearable
activity monitor, which will be used to monitor daily step
count and heart rate. Devices will be paired with a centralized
data aggregation platform which will automatically collect and
store data. Anemia-related symptom and quality of life data will
be assessed using the FACT-An questionnaire at baseline
and then twice a week during the study period. Feasibility will
be measured by accrual rate, Fitbit compliance rate and study
completion rate. Acceptability will be measured by a
satisfaction survey and a brief interview at the end of 3-month

study.

**Objectives:** Primary:

• To assess the feasibility and patient acceptability of using a Fitbit to monitor daily step count and heart rate.

Secondary:

• To graph changes in daily step count, average daily resting heart rate, Fact-An score (assessed before and one day after each transfusion), and hemoglobin level.

Patients will be given an activity tracker to wear continuously

**Population:** Red blood cell transfusion dependent patients with MDS

Phase: Pilot Study

Number of Sites: 1 site (TJUH)

,

**Intervention:** for 90 days

**Description of** 

Study Duration: 12 months

Participant 90 days

Participation Duration:

**Estimated Time to** 

9 months

Complete Enrollment:

# **Schematic of Study Design:**

# Prior to/At Enrollment

Screen potential participant by inclusion and exclusion criteria; obtain informed consent; obtain history, document.

# Baseline/ Enrollment

Perform baseline assessments. Provide patient with Fitbit wearable device. Instruct patient on device utilization. Administer baseline FACT-An questionnaire

# Routine Care

Obtain twice weekly CBCs and receive transfusions per standard of care.

# Twice a week

Complete FACT-An questionnaire. Assess adherence with device.

**Study Completion** 

#### 1 Introduction

#### 1.1 **Background Information**

The myelodysplastic syndromes (MDS) are clonal blood cancers characterized by ineffective blood cell maturation, peripheral blood cytopenias, and risk of progression to acute myeloid leukemia (AML). Effective treatments for MDS are lacking, and the overall prognosis is poor. Every year there are ~15,000-20,000 new cases of MDS in the US, with an incidence that increases very significantly after age 65 . A TriNetX database query shows that at least 275 patients with MDS were seen in the Jefferson Health Network in the past 12 months. The SKCC has identified MDS as a catchment area priority and an enterprise-wide effort is underway to harmonize care and increase access to high impact clinical trials.

The majority of patients with MDS are anemic at diagnosis and become dependent on red blood cell (RBC) transfusions to maintain the hemoglobin at a level that is adequate for oxygen delivery. Frequent RBC transfusions are associated with iron overload, transfusion reactions, alloantibody development, infection, and decreased healthcare related quality of life (HRQoL) . In addition, RBC transfusions significantly increase the cost of care, with one study estimating a >\$30,000 increase in annual cost for MDS patients who are RBC transfusion-dependent compared to those who are not .

The decision to transfuse RBCs in a patient with MDS is often guided by pre-determined hemoglobin threshold levels and modified based on patient symptoms and comorbidities . However, data to support these threshold levels in MDS are scarce. In addition, neither the objective clinical benefit nor the patient-reported symptom improvement associated with transfusion practices based on these hemoglobin threshold levels have been well described. Patient reported outcome (PRO) measures for anemia, such as The Functional Assessment of Cancer Therapy-Anemia (FACT-An), exist, but have not been widely adopted in the care of transfusion dependent patients with MDS. Therefore, the development of a reliable composite decision support tool that includes objective measurements of patient activity, hemoglobin levels, and PRO to guide RBC transfusion practices in patients with MDS would represent a significant advancement.

# 1.2 Rationale for the Proposed Study

Wearable activity trackers, such as Fitbit, Apple Watch, and Garmin, have gained mainstream popularity and are capable of collecting physiologic data like step count and heart rate. Incorporating activity tracker data into oncology clinical trials has been shown to be feasible (measured by device compliance), well tolerated (based on patient survey data), and effective in providing detailed information about patient activity patients with breast, prostate, or endometrial cancer . However, published studies of activity tracker monitoring in MDS patients are lacking.

The primary objective of this pilot study is to test the feasibility and acceptability of using a wearable activity tracker to monitor transfusion dependent MDS patients seen in the SKCC Leukemia/MDS clinic in Center City Philadelphia. In addition, we will generate preliminary data regarding daily step count, average daily resting heart rate, anemia related symptoms, and hemoglobin level. The hypothesis of this study is that patients will be able to comply with device utilization and will find this technology to be an acceptable addition to their care. Ultimately, our goal is to utilize activity tracker data, either alone or in combination with hemoglobin level and/or FACT-An score, to develop a more personalized approach for RBC transfusion in patients with MDS.

#### 1.3 Potential Risks and Benefits

#### 1.3.1 Potential Risks

The potential risks associated with this study are minimal.

#### 1.3.2 Benefits

The benefits of this research study include the acquisition of knowledge about the feasibility of activity tracker use in MDS patients and the correlation between activity level and anemia. Participants will also benefit from the receipt of an activity tracker that they will be able to keep after the study concludes. Although study participants cannot be guaranteed that they will further benefit from the study, the information gained may benefit cancer patients in the future.

# **Study Objectives**

# 1.4 **Objectives**

# 1.4.1 **Primary**

 To assess the feasibility and patient acceptability of using a Fitbit to monitor daily step count and heart rate.

# 1.4.2 Secondary

 To graph changes in daily step count, average daily resting heart rate, Fact-An score (assessed twice a week), and hemoglobin level.

# 1.5 **Endpoints/Outcome Measures**

#### 1.5.1 **Primary**

 Feasibility will be measured by accrual rate, compliance with the device (80% of the 90-day intervention time), and retention rate.  Acceptability will be measured by a short survey and interview addressing participant satisfaction.

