# 3 Study Enrollment and Withdrawal

# 3.1 Eligibility Criteria

#### 3.1.1 Inclusion Criteria

Individuals must meet all of the following inclusion criteria in order to be eligible to participate in the study:

- Confirmed pathologic diagnosis of MDS
- Requiring ≥2 blood transfusions in the past month if previously diagnosed or hemoglobin ≤8g/dL if newly diagnosed
- Age ≥ 18
- ECOG performance status of 0 to 2
- Ambulatory (use of a walking aid, such as a cane or rollator, is acceptable)
- Able to give informed consent
- Willing to comply with all study procedures and available for the duration of the study
- Able to read and/or understand English

- Have access to an iPhone 4S or later, iPad 3 generation or later, Android 5.0 or later, or Windows 10 device.
- Have access to Bluetooth LE and internet connection for syncing.

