#### 9 Statistical Considerations

#### 9.1 **Analysis Plans**

**Primary Analysis:** The first aim of this study is to assess the feasibility of activity monitoring. This will be defined as usage of the Fitbit device for at least 80% of the 90 days under observation. The overall study period compliance rate along with a one-sided exact 95% confidence interval will be estimated. The device will be considered to have acceptable feasibility if the lower bound of the CI is above 0.6 or, equivalently, if at least 17/21 (81%) of participants are compliant for at least 70% of the days under observation.

Accrual rate and retention rate for the study will also be calculated.

Quantitatively, participants will complete the Client Satisfaction Quesionnaire-8 item version (CSQ-8), a validated measure that elicits the client's perspective on the value of services received. Qualitatively, we will interview each participant at the end of their 90-day participation to understand their perceived barriers and facilitators of using Fitbit in their daily activities and elicit their feedback to refine future study design. Interviews will be digitally audio-recorded and transcribed verbatim. Transcripts will be analyzed with a pre-defined code book to summarize participant's experience and comments.

**Exploratory Analyses:** Descriptive statistics will be used to outline patient characteristics and report Fact-An results. We will plot daily step count, average daily resting heart rate, hemoglobin levels, and Fact-An scores. We will use multivariate analyses to identify relationships between these variables and to determine if pretransfusion step count and/or heart rate predict post-transfusion FACT-An results.

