#### 13.3 **Types of Data**

Types of data that will be collected include: laboratory (hemoglobin), transfusion date, number of units of blood transfused, outcome measure data (FACT-An questionnaire, daily step count, average daily resting heart rate, and compliance with wearable device). Reports to monitor enrollment will occur on an ongoing biweekly basis by the study team. Plans for data analysis and interim and final study reports will occur immediately after completion of data collection.

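### The compliance endpoint ignores when wear days fall, so a pass does not show that wear lasted 90 days or that data exist shortly before transfusions

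*Combined protocol and SAP*

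**What the plan says.** Section 1.5.1 names accrual as a feasibility measure, together with "compliance with the device (80% of the 90-day intervention time), and retention rate". Section 9.1 defines feasibility again: "This will be defined as usage of the Fitbit device for at least 80% of the 90 days under observation". The decision follows: "The device will be considered to have acceptable feasibility if the lower bound of the CI is above 0.6". Section 9.1 treats this as the same as passing "if at least 17/21 (81%) of participants are compliant for at least 70% of the days under observation". The last clause uses 70%, not 80%.

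Accrual and retention are to be calculated, but they have no threshold and no part in the decision. No section sets a longest permitted gap, a requirement for wear late in the 90 days, or a requirement for wear around transfusions. No section defines a wear day by hours worn.

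Two places look beyond daily monitoring. Section 1.2 states the eventual aim of using tracker data "to develop a more personalized approach for RBC transfusion in patients with MDS". The exploratory analyses in 9.1 are meant to "determine if pretransfusion step count and/or heart rate predict post-transfusion FACT-An results". On the data side, section 13.3 lists "transfusion date, number of units of blood transfused", and section 13.2 has step count, heart rate and compliance held electronically on the aggregation platform.

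**The concern.** A total of wear days cannot tell scattered missed days from a block of them. Two patterns matter here.

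- **Late stopping.** Section 2 asks for continuous wear over 90 days. A participant who takes the device off for good in the last weeks can still be compliant. Retention does not reveal this, because someone who stops wearing the device but stays in the study is still retained.
- **Gaps before transfusions.** The exploratory analysis uses step count and heart rate from before each transfusion. If the missed days fall there, a compliant participant contributes little to it.

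In either case the study could report acceptable feasibility without knowing whether wear lasted, or whether the data for the next step exist.

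**Working it through.** **The plan's own figures.** Inputs from 9.1 and 9.2: N = 21, null rate 0.60, alternative 0.85, one-sided exact test at 0.05, pass at 17 or more.

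- Power: P(X ≥ 17 | 21, 0.85) = 0.8025, matching the stated 80%.
- Size: P(X ≥ 17 | 21, 0.60) = 0.0370. A cut-off of 16 would give 0.0957, so 17 is the right count.
- One-sided exact 95% lower bound for 17/21 = 0.616, above 0.6.

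The test is sound. What follows concerns what counts as compliant within it.

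**Late stopping.** Each day is treated as worn or not worn.

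- At 80%: 0.80 × 90 = 72 days needed; 90 − 72 = 18 may be missed. Wear on every one of days 1 to 72 and none afterwards is compliant. If all 21 did this, the result would be 21/21.
- At 70%: 0.70 × 90 = 63 days needed; 27 may be missed. The last wear day could be day 63.

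This needs no assumption beyond the choice of threshold.

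**Gaps before transfusions.** Two inputs are missing from the documents: the length of the pre-transfusion window and the number of transfusions during the 90 days. Both are therefore varied. For non-overlapping windows of w days, the largest number of transfusions with a completely blank window is the whole-number part of (missable days ÷ w).

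| Window | 80% rule (18 missable) | 70% rule (27 missable) |
|---|---|---|
| 1 day | 18 | 27 |
| 2 days | 9 | 13 |
| 3 days | 6 | 9 |
| 7 days | 2 | 3 |

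The nearest the documents come to a transfusion count is the entry criterion "Requiring ≥2 blood transfusions in the past month if previously diagnosed". Newly diagnosed patients enter on hemoglobin instead. If the minimum of 2 a month continued, there would be about 2 × 3 = 6 in 90 days, and 18 ÷ 6 = 3, so all 3 days before each could be blank. Other counts change the picture at 80%:

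- 13 transfusions: 18 ÷ 13 = 1.4, so one full day before each.
- 26 transfusions: 18 ÷ 26 = 0.7, so not even one day before each.
- 6 transfusions with a 7-day window: 6 × 7 = 42 days would have to be missed, more than the 18 allowed.

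**Range of coverage.** Count a transfusion as covered if at least 2 of the 3 preceding days have data, and take 6 transfusions.

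- Lowest: 0%, with all 18 missed days in the windows. On this measure two missed days are enough to lose a transfusion, so up to 18 ÷ 2 = 9 could be lost.
- Highest: 100%. The windows occupy 6 × 3 = 18 days, leaving 72 others that can hold the 18 missed days.
- Missed days at random: [C(72,3) + C(72,2) × 18] ÷ C(90,3) = (59,640 + 46,008) ÷ 117,480 = 0.899, about 90%.

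**The case against.** The strongest reply is that the endpoint fits its objective. Section 1.4.1 asks whether a Fitbit can be used to monitor daily step count and heart rate, and a share of days answers that. Transfusion guidance is an eventual goal in 1.2, and the pre-transfusion analysis is exploratory. The plan nowhere says that 17/21 establishes feasibility for guiding transfusion. This stands, and it keeps the point small.

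The plan also has other views of wear: daily plots (9.1), compliance checks at visits and through the platform (4.4), weekly review of activity logs (section 11), and exit interviews. These could show gaps or fading. None of them yields a summary figure or enters the decision, so they lessen the gap without closing it.

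Third, the extreme cases are artificial. Stopping after day 72 requires perfect wear until then. Gradual fading throughout would push many participants below 72 days, so the 80% rule gives some protection. A reader might also infer that patients remove the device when they are weakest, just before a transfusion. Nothing in the documents says so, or says that wear declines with time. The calculations show what the rule permits, not what is likely.

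**Conclusion.** The point holds as a limitation of what a positive result shows. Compliance is a total, and it can be met by participants who all stop for good after day 72 (80%) or day 63 (70%). It also does not show whether data exist shortly before transfusions: under the 80% rule with 6 transfusions and a 3-day window, coverage for a compliant participant can lie anywhere from 0% to 100%, and is about 90% if the missed days are random.

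The late-stopping figures follow directly from the thresholds. The pre-transfusion figures rest on an assumed window and transfusion count.

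A reader might infer that the device could pass with no data before any transfusion. The documents do not support this as a general statement. A participant with 72 wear days has data, and complete blanking is possible only for short windows and limited numbers of transfusions. Nor does the point invalidate the 17/21 rule: the test, N and power stand for the daily-monitoring objective. It is an optional to minor improvement.

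**What to change.** Reconcile the 80% and 70% thresholds in 1.5.1 and 9.1, and keep the 17/21 rule. Add two descriptive feasibility results to 9.1:

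1. The share of transfusions with device data in a pre-specified window before the transfusion date, for example at least 2 of the 3 preceding days. Give a confidence interval that allows for several transfusions per participant. The 2-of-3 rule is only an illustration; the team should choose the window that its exploratory analysis will use.
2. The share of participants wearing the device in each study week, including the last 30 days (days 61 to 90), with the denominator stated.

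Interpret the pre-transfusion analysis, and any statement about use for transfusion guidance, in the light of result 1.

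The cost is a few lines of wording and two tables. Wear data and transfusion dates are already collected, so no participants, visits or procedures are added. The drawback is a little more analysis, and a feasibility picture that may look less favourable than the single rate.

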#### 1.5.2 **Secondary**

- Daily step count
- Average daily resting heart rate
- Fact-An score (assessed twice a week)
- Hemoglobin level measured by CBC twice a week

# 2 Study Design

This is a single arm, prospective, observational pilot study that will collecting data on daily step count, heart rate, and anemia related symptoms. The study population will include RBC transfusion dependent MDS patients who are ambulatory and in the outpatient setting. Patients will be given a wearable activity monitor and instructed to wear it continuously for 90 days. Baseline FACT-An questionnaire will be obtained to assess anemia related symptom data. Patients will have their CBC checked two times weekly and a FACT-An questionnaire will be administered twice a week (either on paper or electronically, based on patient preference). Activity data will be automatically collected from the Fitbit and stored using a centralized data aggregation platform. We will aim to collect data on 21 patients, with an estimated enrollment period of 9 months.

# 3 Study Enrollment and Withdrawal

# 3.1 Eligibility Criteria

#### 3.1.1 Inclusion Criteria

Individuals must meet all of the following inclusion criteria in order to be eligible to participate in the study:

- Confirmed pathologic diagnosis of MDS
- Requiring ≥2 blood transfusions in the past month if previously diagnosed or hemoglobin ≤8g/dL if newly diagnosed
- Age ≥ 18
- ECOG performance status of 0 to 2
- Ambulatory (use of a walking aid, such as a cane or rollator, is acceptable)
- Able to give informed consent
- Willing to comply with all study procedures and available for the duration of the study
- Able to read and/or understand English

- Have access to an iPhone 4S or later, iPad 3 generation or later, Android 5.0 or later, or Windows 10 device.
- Have access to Bluetooth LE and internet connection for syncing.

#### 3.1.2 Exclusion Criteria

An individual who meets any of the following criteria will be excluded from participation in this study:

 Uncontrolled illness including, but not limited to, symptomatic congestive heart failure, unstable angina pectoris, cardiac arrhythmia, or psychiatric illness/social situations that would limit compliance with study requirements

# 3.2 Strategies for Recruitment and Retention

Participants will be recruited from the Department of Medical Oncology- Jefferson Health. Advertisements will not be used to recruit patients for this study other than the Jefferson website. Patients who meet eligibility criteria will be invited by their physician to participate in the study. The study will be discussed with the patient and the patient's questions will be answered to the patient's satisfaction. Patients will be asked to read and comment/ask questions about the study and then sign the informed consent form before any study procedures take place.

# 3.3 Participant Withdrawal

#### 3.3.1 Reasons for Withdrawal

Participants are free to withdraw from participation in the study at any time upon request or dropped from the trial at the discretion of the investigator.

An investigator may terminate a study participant's participation in the study if:

- The subject withdraws consent.
- Investigator's decision to withdraw the subject.
- Noncompliance with trial procedure requirements.
- Administrative reasons
- Any clinical adverse event (AE), laboratory abnormality, or other medical condition or situation occurs such that continued participation in the study would not be in the best interest of the participant.
- The participant meets an exclusion criterion (either newly developed or not previously recognized) that precludes further study participation.

